### **7.3 Procedures to release data or specimens**

In order to access data, a research proposal that describes the intended use of the data must be submitted and approved by the PI. Anyone requesting access to data must obtain IRB approval and demonstrate secure data storage prior to receiving a de-identified data set. Access to the data is limited to non-commercial use.

## **8.0 Sharing of Results with Subjects**

Individual-level data (the results of both COVID-19 tests and the omega-3 levels from the blood draw if applicable) will be shared with participants. The major findings of the study and aggregate data, will be shared with participants after the study has concluded.

1) Unblinding will occur when a subject drops out of the study due to an adverse event. The subject will be informed of their study arm assignment via email so that they can better understand any possible adverse reaction to the study medication.

2) Subjects who complete the study will be unblinded and informed of their study arm assignment via email after the study team has seen their data (descriptive statistics generated by RedCap). This will be done within 4 weeks of each subject finishing the study.

The study coordinator will inform each subject when they finish study participation, to expect an email advising which study arm they were in.

## 9.0 Study Timelines

Each subject will spend 12 weeks in the study.

It is anticipated that all subjects will be enrolled within a 6-month timeframe.

	Month 1	Month 2	Month 3	Month 4	Month 5	Month 6	Month 7	Month 8	Month 9	Month 10	Month 11	Month 12
IRB approvals & startup	X	X	X									
Enrollment				X	X	X	X	X				
Subjects on study (12 weeks)				X	X	X	X	X	X	X	X	X
Interim analysis at 3 weeks					X							
Final data analysis										X	X	X

## 10.0 Inclusion and Exclusion Criteria

### Inclusion Criteria

- Team member at Hackensack Meridian Health
- Age: 18+
- Willing to provide informed consent
- Formal diagnosis of COVID-19 via PCR test (if home test was done, team member must confirm via PCR test)
- Outpatient treatment only for covid-19; no hospitalization (most team members will be vaccinated and may likely have milder case)
- Must be experiencing 1+ ongoing covid-19 symptom being measured in this study (respiratory symptoms (shortness of breath, cough), fatigue, loss of taste, loss of smell)
- Symptom(s) have persisted for more than 12 weeks after initial infection

- Symptom(s) coincided with covid-19 infection and were not present prior to covid-19 infection
- Does not have soy allergy
- Does not have allergy to fish
- Able to participate in bi-weekly surveys in REDCap
- Able to take own blood pressure and record it in bi-weekly REDCap survey
- Willing to participate in 12-week study and be assigned to either intervention or placebo arm
- Not currently taking an omega-3 supplement or other high-dose supplement (over 2,000 IU) with potential for aiding recovery of long covid syndrome (e.g. zinc, Vit C, Elderberry).
- Able to take/swallow six mini-pills daily
- Able and willing to give a spot blood sample (2 drops) at baseline and end of study.

### **Exclusion Criteria**

- Not a Team Member at Hackensack Meridian Health
- Not age 18+
- Unwilling to provide informed consent/ declined to take part
- No formal diagnosis of COVID-19 via PCR test (if home test was done, team member must confirm via PCR test)
- Were hospitalized for treatment of covid-19
- Not experiencing 1+ ongoing covid-19 symptom being measured in this study (respiratory symptoms (shortness of breath, cough), fatigue, loss of taste, loss of smell)
- Symptom(s) have persisted for more than 12 weeks after initial infection
- Symptom(s) did not coincide with covid-19 infection and were present prior to covid-19 infection
- Does have soy allergy
- Does have allergy to fish
- Not able to participate in bi-weekly surveys in REDCap
- Not able to take own blood pressure and record it in bi-weekly REDCap survey
- Not willing to participate in 12-week study and be assigned to either intervention or placebo arm
- Currently taking an omega-3 supplement or other high-dose supplement (over 2,000 IU) with potential for aiding recovery of long covid syndrome (e.g. zinc, Vit C, Elderberry).
- Unable to take/swallow six mini-pills daily
- Not able and not willing to give a spot blood sample (2 drops) at baseline and end of study.

### **11.0 Vulnerable Populations**

Subjects will be age 18+ and must be actively employed by HMH in order to participate in the study.

Hackensack Meridian *Health* is dedicated to creating an inclusive environment that delivers culturally competent, patient-centered care. We value and celebrate the contribution of our team members and acknowledge that everyone deserves to be treated with dignity and respect. Through the Diversity & Inclusion program, we strive to:

- Foster an inclusive environment that embraces different perspectives and that values the contributions of each individual
- Promote diversity at every level throughout our network
- Employ and develop the finest talent from all groups within our vibrant communities
- Provide outstanding and award-winning health care services

Through the Team Member Resource Group (TMRG) strategic initiative of Diversity & Inclusion, team members can link up with coworkers from similar backgrounds and identities to make a difference in the workplace and help achieve their goals. Current TMRGs include the Multiracial Resource Group, Aspiring Women Leaders, Women in Leadership, Pride & Allies, Veterans, and Young Professionals.

To foster diversity in study enrollment, the recruitment flyer will be sent specifically to these TMRGs for targeted distribution.

## **12.0 Local Number of Subjects**

The number of subjects will be 50 in each of two arms, for a total of 100 subjects for analysis. Up to 60 participants in each arm will be recruited if needed, dependent on attrition, for a total of up to 120 subjects.

## **Study Site(s)**

Research activities will take place remotely as indicated. Specifically, subjects will:

- have study meds delivered to them
- will complete eConsent in REDCap
- will have the omega-3 level test kits mailed to their home, will complete the spot blood sample at home and mail directly back to OmegaQuant Lab in the mailing envelope provided.

## **13.0 Recruitment Methods**

Eligible participants will be identified among adult (age 18+) team members working for Hackensack Meridian Health. A recruitment flyer will be sent to all team members via HMH employee newsletters including "The Pulse" and "One." Additionally, to foster diversity in study enrollment, the recruitment flyer will be sent to the Team Member Resource Groups (TMRGs) at HMH for targeted distribution to help ensure diversity in enrollment, as noted in Section 11.0.

The flyer will also be placed in physician lounges across the HMH network.

To further expand recruitment, the study flyer will be given to the HMH Covid Call Center so team members who are experiencing long covid symptoms can be provided with the study email address. Those who receive the email address may contact the study team or not per their preference, and will not be followed up on by the Covid Call Center.

Each potential subject will access a link to an eligibility survey to determine if they meet inclusion criteria.

They will be given the opportunity to ask any questions by contacting a member of the study team. If the team member is interested, they will access the informed consent form in REDCap and be asked to either sign it and participate or download a copy to review on their own time. If they later choose to participate, they can continue with informed consent in REDCap.

Alternatives to participation include that subjects may choose to consult their healthcare provider for help addressing their symptoms. Subjects may also take a supplement(s) on their own at any time.

#### **14.0 Withdrawal of Subjects**

If a subject needs to be withdrawn from the study without their consent for medical reasons or non-compliance, she or he will be notified by [name] or [name] by phone, with a follow-up letter mailed to the subject's home.

If a subject chooses to withdraw from the study, she or he must notify the PI by calling the phone number on the consent form. All data collected up to the point of termination will be kept in the study.

Any subject missing both daily doses 3 times a week for 3 weeks in a row will be removed from the study for non-compliance, and asked to dispose of any unused study supplement/placebo.

#### **15.0 Risks to Subjects and Monitoring Plan**

##### 8 Possible Risks from Omega-3 Supplement:

Risk #1: Taking large amounts of fish oil can inhibit blood clot formation, which may increase the risk of bleeding and cause symptoms such as nosebleeds or bleeding gums

Outcome - Fish oil supplementation did not increase perioperative bleeding [36]

Outcome - The present overview found no support for discontinuing the use of n-3 fatty acid treatment before invasive procedures or when given in combination with other agents that affect bleeding [37].

Monitoring Plan for bleeding risk: *Plan: As bleeding risk is low, we do not need to adjust any medications. We will add a follow up question for each subject, asking: "any bleeding?"*

Risk #2: One small study, for example, found that taking 8 grams of omega-3 fatty acids per day led to a 22% increase in blood sugar levels in people with type 2 diabetes over an eight-week period [38].

Taking high doses of omega-3 fatty acids can stimulate glucose production, which may lead to increased blood sugar — though the scientific evidence is not conclusive.

Monitoring Plan for Hyperglycemia risk: *Chance is low so no need of adjustment of medication required, so we can skip extra monitoring*

Outcome - Findings from RCT trials suggest that omega-3 supplementation was unable to affect either plasma glucose levels or HbA1c except increased fasting glucose levels in Asians [39]

Risk #3: Omega-3 fatty acids have been shown to lower blood pressure, which may interfere with certain medications and cause problems for those with low blood pressure

An analysis of 31 studies concluded that taking fish oil can effectively lower blood pressure, especially for those with high blood pressure or high cholesterol levels [40].

Monitoring Plan for Hypotension risk: *No significant drop to adjust medication. Subject will be asked to self-monitor blood pressure and report it in the bi-weekly survey in REDCap. This RedCap survey also includes a question asking team members to indicate the method used to take their blood pressure: "BP was taken by machine at home" or "BP was taken by machine at a pharmacy" or "BP was taken manually in medical office."*

Outcome: The meta-analysis also found that among all participants who received omega-3s, through supplements such as fish oil, the average decrease in systolic pressure was 1.75 mm Hg and diastolic pressure dropped by 1.1 mm Hg, regardless of the person's blood pressure status [41].

Risk #4: Diarrhea is a side effect of omega-3 fatty acid supplements such as fish oil and flaxseed oil [42].

Monitoring Plan for Diarrhea risk: there is risk of diarrhea with omega-3, taking supplements with meals and consider decreasing dosage to see if symptoms persist. *Will recommend that supplement/placebo be taken with food.* [43]

Risk #5: Fish oil is high in fat and may cause acid reflux symptoms such as belching, nausea, indigestion and heartburn in some people [44].

Monitoring Plan for GERD risk: *Plan: splitting dose into a few smaller portions throughout the day may help eliminate indigestion*

Risk #6: Some animal studies have found that a high intake of omega-3 fatty acids could increase the risk of hemorrhagic stroke while other human studies have found no association [43]

Monitoring Plan for Hemorrhagic stroke: not proved in humans, so will not use this for our study

Risk #7: Caution---Certain types of omega-3 fatty acid supplements like cod liver oil are high in vitamin A, which can be toxic if consumed in large amounts

Monitoring Plan for Vitamin A hypervitaminosis: based on composition, we can also remove this based on our Omega 3 supplement

Risk #8: Although moderate doses of fish oil have been shown to improve sleep quality, one case study suggests that taking large amounts caused insomnia [43].

Monitoring Plan for Insomnia: not including, as there is not enough evidence

Summary of monitoring plan for side effects:

1. Self-reported BP check, submitted via bi-weekly survey, using a BP machine at home, BP machine at a pharmacy, or manually in medical office (will indicate method on bi-weekly survey)
2. Take omega 3 with meals to reduce diarrhea
3. Ask question “any increased bleeding?” during weekly check-in call

Note: *Consent form will include that some interactions may occur with anticoagulants, and antihypertensive medications, though minimal. The consent form will also include that the finger prick spot blood test for omega-3 levels may cause minor soreness on the subject's finger.*

Additionally:

EPA+ DHA is an omega-3 supplement, which are generally regarded as safe when given orally. Omega-3 products are approved for use in the treatment of post myocardial infarction, hypertriglyceridemia and as a dietary supplement in numerous territories worldwide, including Europe and the US.

Experience with the approved preparations and clinical studies is that adverse events are relatively minor in nature and severity, and are primarily related to gastro-intestinal effects.

During the study the subject will take a health survey bi-weekly and will be asked to report any health concerns to the PI. Reported adverse events will be documented. Additionally, the Research Coordinator (RC) will also call each subject weekly for the

duration of the study (total of 12 weeks) to ensure procedures are being followed, answer any questions, and refer any health issues to the PI.

- If any individual subject experiences an adverse event (AE), the PI will determine whether to stop study participation for that individual.
- If the first 10 subjects experience an AE, the study will stop. This decision will be made under the direction of the IRB in consultation with the DSMB as described below in section 19.2 Data Safety Monitoring.

Risks to subjects from Soybean Oil Placebo:

The placebo is made from soybean oil. There is an allergy risk associated with ingesting soy. The study eligibility criteria excludes any person with a soy allergy.

Risks Associated with Washout:

There are no known risks associated with washout from omega-3 supplement or the soybean oil placebo.

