### **19.1.2 Reporting of AEs/SAEs**

AE will be reported and recorded from the time of the first dose of study drug through 30 days after the last dose of study drug. AE monitoring should be continued for at least 30 days following the last dose of study supplement. AEs (including laboratory abnormalities that constitute AEs) should be described using a diagnosis whenever possible, rather than individual underlying signs and symptoms. When a clear diagnosis cannot be identified, each sign or symptom should be recorded as a separate AE. The Investigator should ask the patient non-leading questions to determine if any AEs have occurred during the study, since the last visit. AEs may also be recorded when they are volunteered by the patient, or through physical examination, laboratory tests, or other clinical assessments. An AE should be followed and an assessment should be made at each visit (or more frequently, if necessary) of any changes in severity of the event, the suspected relationship to the study treatment, the interventions required to treat the event, and the outcome.

It is the responsibility of the PI (and/or sub-investigators) to report all unanticipated problems involving risks to subjects or others to HMH IRB.

For unanticipated problems/adverse events associated with clinical trials that do not meet the criteria in Section 19.1.1, the investigator or study team member should describe the events at the time of continuing review.

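### Gastro-intestinal effects, which the protocol names as the main adverse events, get no directed question, while bleeding, rated low risk, is asked about at every weekly call

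*Combined protocol and SAP*

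**What the plan says.** Section 15.0 lists eight risks and closes with a three-line monitoring summary.

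- **Bleeding (Risk #1).** The plan states: "As bleeding risk is low, we do not need to adjust any medications". It continues: "We will add a follow up question for each subject, asking" about any bleeding. The summary then reads: "Ask question “any increased bleeding?” during weekly check-in call".
- **Diarrhea (Risk #4).** The summary line is "Take omega 3 with meals to reduce diarrhea". This is advice to the subject; it asks nothing.
- **Belching, nausea, indigestion and heartburn (Risk #5).** The monitoring plan is that "splitting dose into a few smaller portions throughout the day may help eliminate indigestion". This is again advice, and it does not reach the summary.
- **Overall expectation.** After the summary, Section 15.0 says that "adverse events are relatively minor in nature and severity, and are primarily related to gastro-intestinal effects".

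Section 19.1.2 sets the general method of AE enquiry: "The Investigator should ask the patient non-leading questions to determine if any AEs have occurred during the study, since the last visit". Section 17.1 describes no analysis specific to AEs.

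**The concern.** The plan measures most actively an effect it regards as unlikely and leaves to open enquiry the effects it expects. How often an event is recorded depends partly on how it is asked about, so the side-effect profile will partly reflect the questions.

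This matters because the trial is a feasibility study meant to inform a larger one, and tolerability of six capsules a day bears on acceptability. Answers not sought during the 12 weeks cannot be recovered afterwards.

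**Working it through.** There is no figure in the plan to reproduce. The check is first textual, then a short calculation on assumed rates.

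**1. Effects set against the means of recording them**

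| Effect | Plan's own view | Action in Section 15.0 | Directed question |
|---|---|---|---|
| Bleeding | low risk | question | yes, weekly call |
| Blood pressure fall | no significant drop | self-reported reading | yes, Appendix C |
| Diarrhea | among the main AEs | advice | none found |
| Reflux, belching, nausea, indigestion | among the main AEs | advice, absent from summary | none found |

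Appendix C's symptom grid has rows for shortness of breath, cough, fatigue, taste, smell and Other. Its timed answers are weeks since the covid-19 diagnosis, whereas subjects enter with symptoms lasting more than 12 weeks. A complaint that starts with dosing fits only as an Other symptom still present, or in the comment box. Appendix D asks about ease of taking the pills, interference with daily life, satisfaction and new diagnoses. The diagnosis list has no gastro-intestinal entry.

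**2. Effect of partial capture**

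Let p1 and p0 be the true gastro-intestinal rates on omega-3 and placebo, and c the share of affected subjects recorded, the same in both arms because the arms are blinded and asked the same questions.

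- Recorded difference = c × (p1 − p0), so it shrinks in proportion to c.
- Recorded ratio = (c × p1)/(c × p0) = p1/p0, so it is unchanged.

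All rates and capture shares below are assumptions; 50 per arm comes from Section 12.0.

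| True rates | c = 100% | c = 50% | c = 30% |
|---|---|---|---|
| 20% v 8% | 12 points (10 v 4 subjects) | 6.0 points (5 v 2) | 3.6 points (3 v 1.2) |
| 20% v 10% | 10 points (10 v 5) | 5.0 points (5 v 2.5) | 3.0 points (3 v 1.5) |
| 30% v 10% | 20 points (15 v 5) | 10 points (7.5 v 2.5) | 6.0 points (4.5 v 1.5) |

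**3. Comparing effects with each other**

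Recorded gastro-intestinal to bleeding ratio = true ratio × (gastro-intestinal capture / bleeding capture). Assume true rates of 20% and 5% (ratio 4.0) and bleeding capture of 90%:

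- capture 90%: 0.20 × 0.9 / (0.05 × 0.9) = 4.0
- capture 60%: 0.20 × 0.6 / 0.045 = 2.7
- capture 30%: 0.20 × 0.3 / 0.045 = 1.3

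**4. Link to the stopping rule**

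Section 15.0 halts the study if the first ten subjects have an AE, and the AE definition in Section 19.1.1 has no severity threshold. If the rule means all ten, and subjects are independent with probability p of a recorded AE, the chance of stopping is p to the power 10: 0.001 at p = 0.5, 0.028 at 0.7 and 0.35 at 0.9. The rule is therefore sensitive to how AEs are elicited.

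**The case against.** The strongest reply is that open enquiry does exist. Section 19.1.2 requires active, non-leading AE questions; the coordinator calls weekly and refers health issues to the investigator; Appendices C and D have free text. The weekly call script is not in the documents, so a gastro-intestinal prompt there cannot be excluded. Prompting for a potentially serious event while leaving mild, self-evident ones to open questions is also a defensible choice, and Appendix D, the named instrument for acceptability, already asks about ease and satisfaction directly. All of this stands, and it limits the point to a difference in the mode of asking. It does not make the frequencies comparable.

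A reader might infer more than the documents support:

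- **That gastro-intestinal effects are never asked about.** This is true only of directed questions in the documents.
- **That bleeding is prompted twice a week in two wordings.** Risk #1 announces one question without a frequency, and the summary makes it weekly with the word increased added. It is one question worded inconsistently.
- **That prompted and volunteered events will be pooled in one count.** Section 17.1 is silent on this.
- **That the arm comparison is biased, or bleeding over-represented.** With equal capture the direction and ratio are preserved, and near-complete capture of bleeding is not over-representation.
- **That the cost is a loss of power.** For 20% v 8%, 50 per arm and two-sided 0.05 (sidedness assumed), normal-approximation power is 0.41, 0.21 and 0.14 at 100%, 50% and 30% capture; exact Fisher power is 0.30, 0.09 and 0.03. The plan specifies no AE hypothesis and says it is not powered, so these figures describe no analysis it promises. Even full capture would leave power low.

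**Conclusion.** The point holds as a mismatch between the effects the plan expects and those it asks about directly. Two consequences follow. Recorded frequencies of gastro-intestinal effects and bleeding will not be comparable. If open enquiry misses some gastro-intestinal events, the absolute arm difference shrinks by the capture share, diluted but not reversed. This rests on equal capture in the two blinded arms and on the call script containing no prompt beyond those in the summary. The size cannot be fixed, since the documents give neither event rates nor capture rates; the ranges above are illustrations. It is worth correcting because the correction is cheap and the data feed the planning of a larger trial, but it does not threaten the validity of the randomized comparison.

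**What to change.** 1. Add closed items to Appendix C for both arms on the protocol's own listed effects: diarrhea; reflux, belching, nausea or indigestion; bleeding. Ask for severity (none, mild, moderate, severe) over the past 14 days.
2. Take one reading before the first dose, so that complaints already present are not counted as new.
3. Keep the open AE question of Section 19.1.2 and ask it first, so that the closed items do not lead the answers.
4. Use one wording for the bleeding question throughout; Risk #1 and the monitoring summary now differ (the latter has "any increased bleeding").
5. In Section 17.1, specify a table of solicited effects by arm, separate from volunteered AEs.

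The cost is three or four items and one table. At about a minute per survey (an assumption), six bi-weekly surveys and one pre-dose reading add roughly seven minutes per subject. More mild events will be recorded. The AE definition in Section 19.1.1 and the rule on the first ten subjects in Section 15.0 must therefore be reconciled with the solicited items, and the sponsor should state before enrolment whether solicited events count toward that rule.

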### 19.1 Adverse Events

#### 19.1.1 Definitions

**Unanticipated problems involving risk to participants or others:** Any incident, experience, outcome, or new information that:

1. Is unexpected; and
2. Is related or possibly related to participation in the research; and
3. Indicates that subjects or others are at a greater risk of harm (including physical, psychological, economic, legal or social harm) than was previously known or recognized.

**Unexpected.** The incident, experience or outcome is not expected (in terms of nature, severity, or frequency) given the research procedures that are described in the study related documents, such as the IRB-approved research protocol/research plan and informed consent documents; and the characteristics of the subject population being studied.

**Related.** There is a reasonable possibility that the incident, experience, or outcome may have been caused by the procedures involved in the research.

**Adverse event (AE):** Any untoward medical occurrence in a patient or clinical investigation subject administered a pharmaceutical product and which does not necessarily have to have a causal relationship with this treatment. An AE can therefore be any unfavorable and unintended sign (including an abnormal laboratory finding, for example), symptom, or disease temporally associated with the use of study treatment, whether or not considered related to the study treatment.

**Serious adverse event (SAE):** Any untoward medical occurrence that, at any dose, results in death; is life threatening (i.e., an event in which the patient was at risk of death at the time of the event; it does not refer to an event that hypothetically might have caused death if it were more severe); requires inpatient hospitalization or prolongation of existing hospitalization; results in persistent or significant disability/incapacity; or is a congenital anomaly/birth defect.

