## **19.2 Data Safety Monitoring**

The Hackensack Meridian Health Data and Safety Monitoring Board (DSMB) will be responsible for the data and safety monitoring of this trial. As this study is an investigator initiated feasibility study utilizing a non-FDA approved supplement for which the PI holds the IND it is considered a moderate risk study which requires real-time monitoring by the PI and study team and reviewed monthly by the HMH DSMB.

The Principal Investigator and the Co-Investigators will review the data including safety monitoring at their weekly institution-based meetings and on monthly teleconferences. All Severe Adverse Events (SAEs) are required to be reported to the IRB. Based on SAEs, the IRB retains the authority to suspend further accrual pending more detailed reporting and/or modifications to further reduce risk and maximize the safety of participants. Progress on the trial will be reviewed by the HMH DSMB monthly from the time the first participant is enrolled on the study. Results of the DSMB meetings will be forwarded to the IRB with recommendations regarding need for study closure. DSMB recommendations should be based not only on results for the trial being monitored as well as on data available to the DSMB from other studies. It is the responsibility of the PI to ensure that the DSMB is kept apprised of non-confidential results from related studies that become available. It is the responsibility of the DSMB to determine the extent to which this information is relevant to its decisions related to the specific trial being monitored. A written copy of the DSMB recommendations will be given to the trial PI and the IRB. If the DSMB recommends a study change for participant safety or efficacy reasons, the trial PI must act to implement the change as expeditiously as possible. If a recommendation is made to change a trial for reasons other than patient safety or efficacy, the DSMB will provide an adequate rationale for its decision. Authority to close a trial for safety reasons lies with the IRB, with the above described input from DSMB.

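### The only numeric study-level safety trigger counts any adverse event in either arm and has two readings: one rarely fires even under harm, the other often fires without harm unless background events are rare

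*Combined protocol and SAP*

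**What the plan says.** Section 15.0 (Risks to Subjects and Monitoring Plan) has two stopping provisions. For one person with an adverse event, "the PI will determine whether to stop study participation for that individual". For the study: "If the first 10 subjects experience an AE, the study will stop". The next sentence adds that "This decision will be made under the direction of the IRB in consultation with the DSMB" and points to Section 19.2.

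The terms in that rule are set elsewhere:

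- **What counts.** Section 19.1.1 defines an AE as an unwanted medical event "whether or not considered related to the study treatment".
- **How long.** Section 19.1.2 collects AEs "from the time of the first dose of study drug through 30 days after the last dose of study drug".
- **In whom.** Section 10.0: "Must be experiencing 1+ ongoing covid-19 symptom being measured in this study".
- **How many.** Section 12.0: "The number of subjects will be 50 in each of two arms", with up to 60 per arm if attrition requires it.

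Other study-level safeguards exist. Section 6.2 has an interim look at the first 20 subjects after three weeks, which may lead to a change or closure of an arm. Section 19.2 has weekly review by the investigators, monthly DSMB review and SAE reporting, and says "Based on SAEs, the IRB retains the authority to suspend further accrual". None of these carries a numeric criterion.

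**The concern.** The Section 15.0 sentence is the only place where a number of events leads to a study-level safety action. It counts all-cause events, pooled over omega-3 and placebo, in people who enter with symptoms and are contacted every week. It does not say whether all of the first 10 subjects must be affected, or whether the study stops once any 10 have been.

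The two readings call for different actions. On the first, a single event-free placebo subject among the first 10 keeps the trigger silent whatever happens on omega-3. On the second, everyday complaints from both arms can reach the count with no drug effect. Two people applying the same sentence in good faith could therefore recommend opposite things. A needless stop would also defeat the feasibility objective.

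**Working it through.** The plan gives no operating characteristics for this rule and no AE rate, so there is no figure to reproduce. All rates below are assumptions, shown over a range, and subjects are taken as independent.

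**Inputs from the plan.** Trigger of 10 subjects (Section 15.0); all-cause AEs (19.1.1); 12 weeks of dosing plus 30 days, that is 84 + 30 = 114 days, about 16 weeks (6.1, 19.1.2); two equal arms, 100 subjects or up to 120 (12.0). Section 6.2 does not give the randomisation method, so both a 5/5 split of the first 10 and simple randomisation are shown.

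**Reading 1: all of the first 10 have an AE.** Suppose the strongest possible harm, with every omega-3 subject affected, and let q be the placebo AE rate. With a 5/5 split P = 1^5 × q^5 = q^5. With simple randomisation P = ((1 + q)/2)^10. With no drug effect and a common rate q, P = q^10.

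| Placebo rate q | All omega-3 affected, 5/5 | All omega-3 affected, simple randomisation | No drug effect |
|---|---|---|---|
| 30% | 0.2% | 1.3% | under 0.001% |
| 50% | 3% | 6% | 0.1% |
| 70% | 17% | 20% | 3% |
| 90% | 59% | 60% | 35% |

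For example, 0.5^5 = 0.031 and 0.7^5 = 0.168. With a 5/5 split the placebo rate caps the trigger: no amount of omega-3 harm can lift it above q^5.

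**Reading 2: 10 subjects have had an AE.** P = P(X ≥ 10), where X is the sum of Bin(n, omega-3 rate) and Bin(n, placebo rate), with n = 50 or 60 per arm.

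| Omega-3 rate v placebo rate | 100 subjects | 120 subjects |
|---|---|---|
| 5% v 5% | 2.8% | 7.9% |
| 10% v 10% | 55% | 77% |
| 15% v 15% | 94% | 99% |
| 20% v 20% | 99.8% | above 99.9% |
| 15% v 5% | 55% | 78% |
| 20% v 10% | 95% | 99% |

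At a 5% background, a 10-point omega-3 excess moves the trigger from 2.8% to 55%, so there it does respond to harm. At 15% or more it fires almost surely with or without harm. The 10% v 10% and 15% v 5% rows share a pooled rate of 10% and both give 55%: the count cannot tell the two situations apart.

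**Example replacement: 2 or more of the first 10, or 3 or more of the first 20, with a qualifying event.** Let X1 and X2 be the counts in the first and second ten, each the sum of Bin(5, omega-3 rate) and Bin(5, placebo rate). Then P(pause) = 1 − P(X1 = 0)·P(X2 ≤ 2) − P(X1 = 1)·P(X2 ≤ 1).

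At 5% in both arms: 1 − 0.5987 × 0.9885 − 0.3151 × 0.9139 = 1 − 0.5918 − 0.2880 = 0.120.

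| Qualifying rate, omega-3 v placebo | P(pause) |
|---|---|
| 2% v 2% | 2% |
| 5% v 5% | 12% |
| 10% v 10% | 39% |
| 10% v 2% | 16% |
| 18% v 2% | 39% |
| 20% v 2% | 45% |
| 30% v 2% | 71% |

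**The case against.** The strongest reply is that the sentence does not act alone. The IRB directs the stop with DSMB advice, and the first-20 look, weekly investigator review, monthly DSMB review and SAE reporting all continue. The product's expected events are described as minor and mainly gastro-intestinal, and this is a feasibility study. On that view the text needs only a clarification. The first part stands: the figures are probabilities that the trigger is met, not that the study closes. It does not remove the point, because the text says the study will stop, and Section 19.2 gives neither body a rule for what to count.

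A second reply is that on Reading 2 the trigger can work. This also stands. At a background of about 5% or less it mainly follows omega-3 harm. Whether all-cause AEs over about 16 weeks could be that rare in symptomatic subjects with weekly calls is a judgement, since the documents give no rate.

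A third reply is that any pooled replacement shares the weakness. The example gives 39% both at 10% v 10% and at 18% v 2%. That is correct. Counting only related serious or discontinuing events should lower the background, but sensitivity to arm has to come from the DSMB's unblinded review.

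**Conclusion.** The concern holds in a conditional form. The sole numeric study-level trigger is ambiguous, counts all-cause events and pools the arms. Read literally, it almost never fires unless background AEs are very common: at most 3% at a 50% placebo rate with a 5/5 split, even if every omega-3 subject is affected. Read as a running count of 10, it fires without any drug effect in 55% of trials at a 10% AE rate and 99.8% at 20%, with 100 subjects. These sizes rest on assumed AE rates and independent subjects.

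Three stronger inferences are not supported:

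- **That the trigger follows background more than harm on either reading, whatever the rate.** At low background the running count does respond to harm (2.8% to 55% at 5% v 5% and 15% v 5%).
- **That 35% (a common 90% rate) against 3% (every omega-3 subject affected, 50% on placebo) measures how much more background matters.** Those cases have pooled rates of 90% and (100% + 50%)/2 = 75%. At a common 75% the figure is 0.75^10 = 5.6%, so most of the gap is the unequal pooled rate.
- **That subjects are left unmonitored.** The safeguards in Sections 6.2, 15.0 and 19.2 remain. The fault is in the numeric rule.

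**What to change.** Replace the sentence in Section 15.0 with a trigger that states:

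- **Event counted:** a subject with an SAE that meets the relatedness definition in Section 19.1.1, or with a related AE that leads to stopping study product, counted from first dose.
- **Action:** when the count is reached, enrolment pauses, and dosing too if the DSMB advises. The DSMB reviews the events unblinded by arm, and the IRB then decides under Section 19.2.
- **Interim look:** the existing first-20 look uses the same events.
- **Count:** set by the DSMB. Two of the first 10 or three of the first 20 is an example only.

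The change costs one protocol paragraph. The definitions, the 20-subject look and the DSMB/IRB route are already in the plan. There are downsides. The pooled count still cannot separate the arms by itself. The example pauses 12% of trials at a 5% qualifying rate in both arms and 39% at 10%, and it reaches only 16% at 10% v 2%, so it is not sensitive to moderate harm. Related non-serious events in subjects who stay on product would not count and would rely on the existing reviews.
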